#### **4.3 Enrollment/Procedural Timeout**

Enrollment in either arm of this study will occur at the Procedural Timeout. The Procedural Timeout will be conducted in the operating room, by a trained site investigator, following the completion of the Stage II repair. During the Procedural Timeout, a site investigator will confirm all inclusion and exclusion criteria have been met per Section 4.1 of this protocol and document his/her decision to enroll the subject. If the site investigator determines that the subject, in either arm, fails to meet all inclusion and exclusion criteria, the subject will be declared a screen failure (see Section 4.5) and exited from the study. A subject should not be enrolled in either arm of the study if the subject has surgical complications during the Stage II repair that result in, or could be reasonably expected to result in, significantly decreased cardiac function.

For the treatment group, if a subject is determined to be eligible to enroll, the Procedural Timeout will also include confirmation that the subject's identity matches the patient identifiers on the investigational product label, confirmation of the number of injection sites and product volume to be delivered, and confirmation that there aren't any anticipated complications or concerns.

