#### **4.4 Time of Treatment (Treatment Arm Only)**

For subjects enrolled in the treatment arm, thawing of the product and the cell delivery procedure will occur immediately following the Procedural Timeout. A subject is considered treated at the time that cell delivery injections begin. If only a partial cell delivery occurs, the subject will still be considered treated and will be followed as planned according to the procedures described in

Section 6 of this protocol. The cell delivery procedure will be entered in the eCRF and the reason(s) for failing to deliver a full dose, if applicable, will also be documented in the eCRF.

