#### **5.4.2 Product Administration**

Prior to thawing the cells, the identity of both the product and the subject will be confirmed by the study team at the time of enrollment. Following enrollment, trained and delegated team member(s) will thaw the investigational product within the surgical suite. Once thawed, the pre-calculated volume (see Section 5.3) of UCB-MNC product will be loaded into a 1 mL syringe fitted with a 27-gauge butterfly needle and handed off to a site investigator for the cell delivery procedure. The product delivery into the heart tissue should begin within 30 minutes from the beginning of product thawing.

The cell delivery will be performed with injections directly through the epicardial surface of the myocardium, within the free wall of the right ventricle, avoiding epicardial vessels.

Approximately 0.1mL will be delivered per injection site, over 5-10 seconds, followed by 20 seconds of rest prior to needle withdrawal to maximize cell retention within the myocardium. Direct visualization will ensure the cell-based product is entering the myocardial wall and not entering into the ventricular lumen or coronary vessels or being displaced backwards through the injection site upon removal of the needle. The injection sites will be spaced approximately 1 cm apart from each other across the free wall of the right ventricle. Injection sites will be documented on a diagram to record the approximate location of injection sites relative to the coronary vasculature.

Injections will be halted upon complications such as excessive bleeding, ventricular fibrillation, sustained arrhythmias, low blood pressure requiring pharmacological support, or any other concerns of atypical physiology from anyone on the surgical team; the event(s) will be recorded as adverse event(s) on the applicable eCRF. Total volume delivered will be recorded for all partial (less than the planned cell delivery volume) and complete cell deliveries. If a partial cell delivery has occurred, subjects will continue to be followed as planned according to this protocol. Partial cell deliveries along with the specific rationale will be documented on the applicable eCRF but are not considered to be a protocol deviation.

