### 7.2 Subject Population(s) for Analysis

Only consented and eligible subjects will be used in analysis. Safety analysis will be based upon all subjects who undergo surgery and receive any volume of cell delivery (partial or full) and have follow-up data in the cell-therapy group and all subjects who have follow-up data in the control group. Efficacy analysis will be based upon all subjects who receive full cell delivery and have follow-up data in the cell-therapy group and all subjects who have follow-up data in the control group.

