### 7.4.3 Short Term Efficacy Analysis

#### Primary Outcome

The primary analysis of the primary outcome apical fractional area change 3 months post Stage II palliative surgery will be done using analysis of covariance (ANCOVA), including a model term for the difference in means between the cell-based therapy and control groups, as well as a model term for apical fractional area change at time of surgery to account for subject baseline condition. In secondary analyses of the primary outcome we will, using interaction terms, fit a model allowing the treatment effect (mean difference between the cell-therapy and control groups) to depend on baseline fractional area change.

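### The efficacy set drops partly treated children from Arm A after enrollment, with no matching exclusion of controls, so the 3-month FAC comparison can be biased in favor of cell therapy.

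*Combined protocol and SAP*

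**What the plan says.** Section 7.2 sets the Arm A condition: "Efficacy analysis will be based upon all subjects who receive full cell delivery and have follow-up data in the cell-therapy group". For Arm B the set is "all subjects who have follow-up data in the control group". The safety set in the same section takes Arm A subjects who received any volume.

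The order of events is given in Sections 4.3 and 4.4. "Enrollment in either arm of this study will occur at the Procedural Timeout", which takes place after the Stage II repair is complete. For Arm A, "thawing of the product and the cell delivery procedure will occur immediately following the Procedural Timeout". Section 4.3 also applies one screen to both arms: "A subject should not be enrolled in either arm of the study if the subject has surgical complications during the Stage II repair", where those complications have reduced cardiac function or could be expected to.

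Section 5.4.2 gives the reasons for stopping early: "Injections will be halted upon complications such as excessive bleeding, ventricular fibrillation, sustained arrhythmias, low blood pressure requiring pharmacological support", or other atypical physiology. Section 4.4 keeps these children in the study: "If only a partial cell delivery occurs, the subject will still be considered treated and will be followed as planned".

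The primary analysis in Section 7.4.3 is an ANCOVA of 3-month apical FAC with a group term, "as well as a model term for apical fractional area change at time of surgery to account for subject baseline condition". Section 7 specifies no alternative efficacy set. Section 7.4.1 describes the interim analyses as covering everyone enrolled, while also referring back to the statistical analysis plan.

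**The concern.** Whether delivery was full or partial is known only after enrollment, and only in Arm A. A treated child who becomes unstable during injection leaves the efficacy comparison. A control who becomes equally unstable after the Timeout stays in, provided follow-up data exist. There are two ways this can mislead.

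- **The halt marks a sicker child.** Removing such children from one arm raises the treated mean and creates an apparent benefit.
- **The injection caused the event.** The affected children have no counterpart among controls, and dropping them hides the harm from the FAC estimate.

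Halts unrelated to prognosis cause little or no bias. As worded, Section 7.2 also leaves enrolled Arm A children whose delivery was cancelled out of both the efficacy and the safety set.

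**Working it through.** **1. The plan's own figures.** Inputs from Section 7.1: alpha 0.05, equal variance, 80% power, 50 per arm, or 30 per arm after 40% attrition. Sidedness is not stated. A two-sided two-sample t-test gives detectable effects of 0.566 and 0.736 SD, which round to the stated 0.57 and 0.74. So 0.57 SD is a fair yardstick for bias.

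**2. Formula for the shift.** Let f be the share of complication-prone children, D their deficit in 3-month FAC (in SD, not explained by baseline FAC), and m the mean of the other children. Suppose cells have no effect.

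- All children kept: both arms average m − fD; difference 0.
- Full delivery only, halt marks a sicker child: Arm A averages m, controls average m − fD; difference +fD.
- Full delivery only, injection caused the event: both arms average m; difference 0, although the effect in all treated children is −fD.

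**3. Numbers.** The documents give neither f nor D, so every input below is an assumption. False-positive rates come from simulated ANCOVAs: 20,000 trials per cell, 50 per arm, no true effect, no missing data, complication-prone children equally common in both arms, and baseline-to-3-month correlation 0, 0.5 or 0.7.

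| f | D (SD) | Shift f × D (SD) | Shift / 0.57 | Two-sided false positives, full delivery only (correlation 0 / 0.5 / 0.7) |
|---|---|---|---|---|
| 2% | 0.5 | 0.010 | 1.8% | 5.2 / 5.1 / 4.9% |
| 5% | 0.5 | 0.025 | 4.4% | 5.2 / 4.9 / 5.5% |
| 10% | 0.75 | 0.075 | 13.2% | 6.3 / 6.8 / 7.6% |
| 20% | 1.0 | 0.200 | 35.1% | 13.8 / 17.1 / 21.7% |

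With every complication-prone child kept, the rate is 4.8–5.5% in all cells.

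**4. Injection-caused events** (Arm A only, correlation 0.5). Full delivery only gives an estimate of 0.00 in both cases tried. The any-volume set gives −0.076 (10%, 0.75 SD) and −0.200 (20%, 1.0 SD), close to the true −0.075 and −0.20.

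**5. What any-volume leaves behind.** Suppose 10% are complication-prone, the gap is 0.75 SD, and one fifth of the complication-prone Arm A children are cancelled before the first injection. The remaining share in Arm A is 0.08/0.98, so the bias is 0.75 × (0.10 − 0.08/0.98) = 0.014 SD. Simulation gives 0.013 for any-volume, 0.074 for full delivery only and −0.001 for all enrolled.

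**The case against.** **The window is narrow and the rate may be low.** Section 4.3 screens both arms after the repair, and for Arm A also confirms that no complications are anticipated. At 5–10 seconds plus about 20 seconds of rest each (Section 5.4.2), six injections take roughly 2.5 to 3 minutes plus repositioning. The Phase I text in Section 1.4 mentions one suture-controlled bleed among ten treated children and does not say that delivery was stopped. This stands as a limit on size: at 5% partial delivery or less with a 0.5 SD gap, the bias is trivial. It does not remove the asymmetry, because the screen ends before the first injection.

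**Harm is examined elsewhere.** Section 5.4.2 records halting events as adverse events, and Section 7.4.5 analyzes bleeding and reduced cardiac function separately, with partly treated children included. That is true, but it compares adverse events. It does not restore these children to the FAC contrast.

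**Unstable controls may also drop out.** Section 6.3.2 replaces the clinic visit with a phone call when a child cannot attend safely, so some unwell children in either arm will lack the 3-month echo. This stands, and the actual bias may be smaller than simulated. The follow-up-data condition is nevertheless common to both arms; the delivery condition is not.

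**Efficacy should be judged in properly dosed children.** Section 5.4.2 defines partial by planned volume, which does not track cells per kg. Take the 6.9 kg child of Section 5.3. Five of six injections at 30 million/mL deliver 5 × 0.1 × 30/6.9 = 2.2 million/kg, inside the stated target of 1–3 million/kg, and the child is excluded. Six at 10 million/mL deliver 6 × 0.1 × 10/6.9 = 0.87 million/kg, and the child is included.

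**The interim wording may be only ambiguous.** Section 7.4.1 can be read as deferring to Section 7.2. On either reading the two sections need reconciling.

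**Conclusion.** The concern holds. The one-arm, post-enrollment exclusion is certain from the text. Its direction is upward whenever halted injections mark or cause lower function, and there is no shift if they do neither.

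Its size is unknown. It is negligible at 2–5% partial delivery with a 0.5 SD gap, modest at 10% and 0.75 SD, and serious only at the upper assumption. Small numbers raise the stakes early: at the first interim, one exclusion among ten treated children is already 10% of Arm A, and Section 7.4.2 lets the sponsor conclude from that point on that the endpoints have been met. The plan contains no analysis that would show whether the bias is small or large. It should be fixed before outcomes are examined.

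**What to change.** Amend Section 7.2, and Section 7.4.1 to match:

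1. Make the primary efficacy set all Arm A subjects with any volume delivered against all enrolled controls, with missing echo data handled under Section 7.3 in the same way in both arms.
2. Keep full delivery only as a labelled sensitivity analysis.
3. Report the number of, and reasons for, all partial deliveries and all enrolled Arm A subjects with cancelled delivery or compromised product.
4. Add a sensitivity analysis of everyone enrolled at the Procedural Timeout, by arm, where data exist, because any-volume is itself an Arm A-only condition.
5. Name one efficacy set for both interim and final analyses.

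The cost is SAP wording; follow-up of partly treated children is already planned. The statistical price is some dilution. In the worst case, where partial doses do nothing, 10% partial delivery cuts a 0.57 SD effect to 0.57 × 0.90 = 0.51 and power from about 81% to 72%. At 20% the figures are 0.57 × 0.80 = 0.46 and 62%. Data on cancelled deliveries will be limited, because Section 4.6 discontinues subjects whose product is compromised.

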### 7.3 Statistical Methods

#### Descriptive Statistics

Descriptive statistics (e.g., mean standard deviation, median, minimum, and maximum for numerical data and counts and percent for categorical data) will be calculated, as appropriate for all variables. Baseline values for demographic, clinical, and outcome variables will be described separately for the cell-based therapy and control groups.

#### Handling of Missing Data

Missing data will be addressed using last observation carry forward (LOCF) where appropriate. Where LOCF is not appropriate missing data will be left as missing. Heavy tailed distributions and outliers will be addressed by considering transformations to allow approximate normality of the means. Data will be reviewed for outliers before analysis and values may be checked against source data.

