#### 3.1.2 Subject Evaluation

Once consent has been obtained, subjects will enter the screening phase where a pre-operative baseline work-up will be performed as outlined in Section 6 of this protocol. Following the pre-operative work-up, Stage II surgical repair, and final eligibility confirmation according to the inclusion and exclusion criteria listed in Section 4 of this protocol, the subject will be enrolled on to the trial. Following Stage II surgical repair hospitalization, subjects will enter active follow-up. This includes evaluation in-clinic at 3 and 12-months post-Stage II surgical repair, which will include the collection of imaging data. Phone follow-ups will be conducted at 1 month and 6 months post-Stage II surgery and conducted every 6 months following the 12-month in-clinic visit up to pre-operative work-up for the Stage III Fontan palliative surgery, cardiac transplant or to 4 years post-Stage II surgery, whichever is first.

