### 3.2 Short Term Endpoints

The primary short-term efficacy endpoint regarding the cell product and its delivery procedure is:

Change in right ventricular cardiac function at 3 months post-Stage II surgery compared to baseline, measured by *apical fractional area change, circumferential strain, and longitudinal strain on echocardiogram*.

Secondary short-term efficacy and safety endpoints in order of their relevance and importance in this clinical study are:

- 1) Change in cardiac function between baseline and hospital discharge for Stage II surgery, measured by echocardiogram.
- 2) Cumulative days of hospitalization per patient at 1 and 3-months post Stage II surgery.
- 3) Change in weight, heart rate, and oxygen saturation at 3-months post Stage II surgery compared to baseline.

Additional variables may be assessed in an exploratory manner.

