### **6.3.2 3 and 12 Month In-Clinic Visits:**

- Changes in Concomitant Medications
- AE Assessment
- Physical Exam (including weight)
- Vital Signs (heart rate, blood pressure, oxygen saturation)

- Cardiac Markers (CRP, High Sensitivity Troponin T, NT-proBNP)
- CBC w/ Differential (RBC, WBC, Hemoglobin, Hematocrit, Platelets, Neutrophils, Lymphocytes, Monocytes, Eosinophils and Basophils)
- Liver/Renal Function (ALT, ALP, AST, total bilirubin, albumin, total protein, BUN, creatinine)
- TSH
- Panel-Reactive Antibody (PRA) Test (see Appendix D)
- 12 Lead ECG
- Echo (TTE)
- Questionnaire Completion (12 month visit only)

If a subject is unable to safely attend the 3 month and/or 12 month in-clinic follow-up visit(s), the phone follow-up procedures as described in this protocol will replace the in-clinic visits. Medical records will be obtained to provide evidence of the condition that precludes a subject from safely attending the 3 and/or 12 month in-clinic follow-up visit and local medical doctor notes, if available, will be collected.

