### 7.1 Sample Size Determination

Sample size calculations were performed using alpha = 0.05 and assume equal variance across study arms. With 50 subjects per arm we will have 80% power to detect an effect size as small as 0.57 in difference in cardiac function measures. This is built on the assumption all subjects from both arms have complete data at baseline and 3-month follow-up visits. In the event of attrition or incomplete data in 40% of participants, equal across study arms, the study has 80% power to detect an effect size as small as 0.74 in difference in cardiac function measures.

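### Section 7.3 permits LOCF without saying when, so the primary 3-month FAC analysis is not fixed; separately, a lost child can be counted as a transplant event on an investigator's impression

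*Combined protocol and SAP*

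**What the plan says.** Two sentences in Section 7.3 (Handling of Missing Data) form the whole rule: "Missing data will be addressed using last observation carry forward (LOCF) where appropriate" and "Where LOCF is not appropriate missing data will be left as missing". No criterion, endpoint, visit, decision-maker or timing is given. The secondary analyses in Section 7.4 concern baseline interaction and hospital effects, not missing data.

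The primary analysis (7.4.3) is an ANCOVA of 3-month apical FAC with a treatment term, "as well as a model term for apical fractional area change at time of surgery to account for subject baseline condition". The last scheduled echo before month 3 is at hospital discharge (6.2.3), and Section 3.2 makes that time point its first secondary endpoint: "Change in cardiac function between baseline and hospital discharge for Stage II surgery, measured by echocardiogram".

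Three other places bear on the question:
- Section 7.2: "Efficacy analysis will be based upon all subjects who receive full cell delivery and have follow-up data in the cell-therapy group". Follow-up data is not defined.
- Section 7.1: "In the event of attrition or incomplete data in 40% of participants, equal across study arms", the detectable effect rises from 0.57 to 0.74.
- Section 6.3.2: "If a subject is unable to safely attend the 3 month and/or 12 month in-clinic follow-up visit(s), the phone follow-up procedures as described" replace the visit, so the 3-month echo can be missing for clinical reasons. Under 3.1.2, phone follow-up runs to Stage III work-up, "cardiac transplant or to 4 years post-Stage II surgery, whichever is first".

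The paragraph headed Lost to follow up censors lost subjects in time-to-event analyses, with one exception: if investigators believe transplant could have been indicated, the subject is counted accordingly. No criteria, event date, blinding or adjudication is given.

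**The concern.** Section 7.3 (Multiplicity) makes no correction because there is one primary analysis. With two permitted ways to treat a missing 3-month FAC, that analysis is not fully specified. The study is open-label, efficacy is examined at up to five interim looks (7.4.1), and the sponsor may conclude after any of them that the endpoints are met (7.4.2). The branch could therefore be chosen with results in view.

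LOCF also puts function at discharge into an endpoint meant to measure function at 3 months. If the effect develops after discharge, the estimate is diluted. The plan does not say whether a child who dies or is transplanted before 3 months has a discharge FAC carried forward.

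The censoring exception is a separate defect with a different endpoint and mechanism. It concerns time to listing or death, fifth among the long-term secondary endpoints in Section 3.3, and lets knowledge of the arm enter the event count.

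**Working it through.** **1. The plan's own figures.** Inputs from 7.1: alpha 0.05 (sidedness not stated), 80% power, 50 per arm, 40% incomplete equally by arm. The two-sided normal approximation is (1.960 + 0.842) × √(2/n).
- n = 50: 0.560; with the t distribution 0.566, which rounds to 0.57.
- n = 50 × (1 − 0.40) = 30: 0.723; with the t distribution 0.736, which rounds to 0.74.

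Both figures reproduce. A one-sided test would have about 89% power, so two-sided was evidently used. The 0.74 needs 30 observed subjects per arm, so it treats missing subjects as missing. Under LOCF the missing values would be filled and up to 50 per arm analysed.

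**2. Effect of the branch when treatment works.** The true 3-month effect is 0.57, a fraction m is missing at random in each arm, and a share f of the effect is already present at discharge. Only m = 40% comes from the plan.

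LOCF estimate = 0.57 × (1 − m) + m × f × 0.57. For example, m = 0.4 and f = 0 gives 0.57 × 0.6 = 0.34.

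| Missing | Share at discharge | LOCF estimate | LOCF power | Left-missing estimate | Left-missing power |
|---|---|---|---|---|---|
| 20% | none | 0.46 | 61.7% | 0.57 | 71.1% |
| 20% | half | 0.51 | 71.9% | 0.57 | 71.1% |
| 20% | all | 0.57 | 80.6% | 0.57 | 71.1% |
| 40% | none | 0.34 | 39.5% | 0.57 | 58.4% |
| 40% | half | 0.46 | 61.7% | 0.57 | 58.4% |
| 40% | all | 0.57 | 80.6% | 0.57 | 58.4% |

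Power is for an unadjusted two-sample t-test with unit SD. Baseline adjustment raises it in both branches.

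**3. Choosing the branch afterwards, no true effect.** ANCOVA was simulated with 10,000 replicates per scenario, 50 per arm, assumed correlation 0.6 between visits, equal random missingness and a discharge-to-3-month shift of 0 to 1.0 SD. Each branch alone gives about 5% false positives. Taking whichever is significant gives 6-7% at 10% missing, 7-8% at 20% and 8-9% at 40%. Correlations of 0.4 or 0.8 change little (6-7%, 7% and 8-9%).

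**4. Unequal random dropout, no true effect.** LOCF bias = shift × (control missing − treated missing). With 20% missing in treated and 40% in control, a shift of 0.5 SD gives 0.5 × 0.2 = 0.10 SD and 9% false positives; 1.0 SD gives 0.20 SD and 19%. With 10% v 20%, the same shifts give 0.05 and 0.10 SD, and 6% and 8%. Either equal dropout or no shift removes this bias.

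**5. Dropout related to function, no true effect.** Assumptions: 20% v 40% missing, poorer function more likely missing, shift 0 or 0.5 SD, baseline imbalance 0 to 0.5 SD.
- Driven by the discharge echo: bias +0.02 to +0.13 SD for LOCF, −0.04 for ANCOVA on observed data, and 0.00 for a mixed model on post-baseline echoes with baseline as covariate.
- Driven by the unseen 3-month value: about −0.03 to +0.08 for LOCF, −0.10 to −0.11 for observed-data ANCOVA (8-9% false positives), and −0.09 for the mixed model (7-8%).

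**6. Censoring exception.** Assumed: 10% events and 10% lost per arm over 4 years, no true effect. With 50 per arm that is 5 events and 5 lost in each. Recoding a quarter of lost controls only makes the event ratio about 5/6.25 = 0.80; recoding half makes it 5/7.5 = 0.67. Simulated Cox/log-rank analyses (3,000 replicates) give median hazard ratios of 0.80 and 0.65, with 7% and 10% false positives. With 20% events the ratios are 0.88 and 0.80. Recoding both arms equally leaves 1.00 and 5%; recoding treated children only would push the other way. The simulation runs from surgery and models neither the endpoint's start after the 6-month follow-up nor exit at Stage III work-up.

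**The case against.** The strongest defence is that intent is partly visible: 0.74 is an observed-subjects figure, so the plan may already mean to leave a missing 3-month FAC missing. That stands as evidence of intent, but 7.3 names LOCF first and 7.2 does not settle the matter. Blinded core-lab reading (Appendix B) protects the measurement, and consented collection of standard-of-care echoes (4.6) reduces missingness; neither sets the rule.

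LOCF is also not uniformly worse. If the whole effect is present at discharge, it is unbiased and more powerful. If missingness follows the unseen 3-month value, observed-data ANCOVA can be the more biased method (step 5). Both points stand, so the case for barring carry-forward rests on keeping the endpoint at 3 months and fixing the rule in advance, backed by sensitivity analyses.

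A reader might infer that the plan carries a serious false-positive risk, such as the 19% in step 4. The documents do not support that: it needs both unequal dropout and a large shift, and they show neither. Nor do they show that the censoring exception would favour treatment. They give no event rate, no loss rate and no sign that it would be applied unequally.

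**Conclusion.** The gap is real and should be fixed; it does not invalidate the design. Section 7.3 leaves open whether a missing 3-month FAC is dropped or replaced by a discharge value, and no sensitivity analysis would reveal the difference. The main consequence is dilution of an effect that develops after discharge: 0.57 becomes about 0.46 at 20% missing and 0.34 at the plan's 40% contingency if nothing is present at discharge. Choice of branch alone inflates false positives only modestly (6-9% over 10-40% missing). Apart from the 40%, the missingness rates, correlation, shift and share at discharge are assumptions.

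The censoring exception is a lesser, separate point. It has no criteria and is applied by people who know the arm, but it distorts the hazard ratio only if applied unequally. With few events, one or two children would then matter.

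**What to change.** 1. **7.3, Handling of Missing Data.** State that no echo measure is carried forward. Keep the baseline-adjusted ANCOVA on observed 3-month FAC as primary. Add as a sensitivity analysis a mixed model on post-baseline echoes only (discharge, 3 and 12 months), with baseline FAC and baseline-by-visit as covariates.
2. **7.2.** Define follow-up data: an observed 3-month echo for the primary ANCOVA; for the sensitivity analyses, all enrolled subjects otherwise meeting the efficacy-set criteria, with or without that echo. Without this the sensitivity analyses have no defined population.
3. **Tipping-point analysis.** Apply it to all missing 3-month FAC in the wider set. Report deaths and transplants before 3 months by arm, do not carry their values forward, and give them a stated unfavourable value. Acknowledge that observed-data ANCOVA can be more biased than LOCF if missingness depends on the unseen 3-month value.
4. **7.1.** Say that 0.74 refers to 30 observed subjects per arm.
5. **7.3, Lost to follow up.** Delete the exception based on investigators' belief, count only documented listing or death, and censor lost subjects at last contact.

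The cost is SAP wording and modest programming, with no new visits. Intervals may be wider than LOCF would give.
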